## **Serious adverse events notification:**

The investigator must immediately notify the sponsor on the day that he becomes aware of it of any serious adverse event or any new fact or pregnancy, if it occurs:

- after the date of signature of the consent form,
- at any time during the period of follow-up planned by the study for the participant,

If the investigator becomes aware of a serious adverse event, which he/she suspects is causally related to the research, occurring after the end of the clinical trial in a participant he/she has treated, he/she shall inform the sponsor without delay.

TYPE OF EVENT	NOTIFICATION METHOD	TIME LIMIT FOR NOTIFYING THE SPONSOR
Non-serious AE	In the case report form	No immediate notification
AE of special interest (conjunctivitis)	In the case report form + initial SAE declaration form	Sponsor to be notified immediately
SAE	Initial SAE declaration form + written report if necessary	Sponsor to be notified immediately
New fact	Declaration form + written report if necessary	Sponsor to be notified immediately
Pregnancy	Pregnancy declaration form	On confirmation of the pregnancy

Name of sponsor/Vigilance Unit: CHU de Toulouse [name] [name] [contact]

*E-mail*: [contact]

All these events must be monitored until they are **completely resolved**. The investigator will send the sponsor additional information (additional declaration form) concerning the evolution of the event not mentioned in the initial report.

The investigator and the sponsor must evaluate the causal relationship between the study drugs (dupilumab/placebo) and the SAE, independently. If the SAE is not related to the study drug, the investigator and the sponsor must determine the alternative causality (eczema, concomitant treatment, other pre-existing disease, etc...). If they are not agreed about the final causality assessment, this discrepancy has to be notified in the SAE report.

All SAE that are considered to be reasonably related to the IMP, will be defined as a "serious suspected adverse reaction".

#### **Pregnancies**

Pregnancy occurring during the period or immediately after a study does not constitute an SAE. However, a pregnancy must be notified in the same way as an SAE because it requires particular monitoring throughout its duration. In the event of pregnancy, dupilumab should be immediately discontinued and the pregnancy must be reported immediately of the Investigator's knowledge of it by fax to the Sponsor using the Pregnancy Reporting Form.

The Investigator will follow the female subject until completion of the pregnancy, and must notify the Sponsor of the outcome of the pregnancy immediately when having knowledge of the outcome using the Follow-Up Pregnancy Reporting Form.

Any anomaly observed in the foetus or child will then be notified. Any elective termination of pregnancy (ETP), medical termination of pregnancy (MTP) or spontaneous abortion must give rise to a notification of pregnancy, and if it necessitated hospitalisation, it must be passed on in the same manner as an SAE.

# 12.4. DECLARATION AND RECORDING OF UNEXPECTED SERIOUS ADVERSE REACTIONS AND NEW FACTS

The sponsor/vigilance unit immediately declares any **SUSAR** occurring during the study:

- to ANSM [the French Agency for the Safety of Health Products],

In addition, the sponsor/vigilance unit will record all SUSAR in the EudraVigilance database.

In the event of blinded research, the sponsor declares any SUSAR after unblinding.

The sponsor/vigilance unit shall declare without delay **new facts** that have arisen during the research to:

- the ANSM,
- the Committee for the Protection of Persons,

The sponsor and the investigator will take the appropriate urgent measures. The sponsor will inform the competent authority and the committee for the protection of persons.

## Summary table of declarations by type of study

	Declaration to			
Type of study and type of AE	Competent authority	app.	Initial declaration period	Follow-up period
type of AE	(EMA, ANSM, etc.) CPP peri		periou	
Drug: SUSAR			- death or life- threatening: without delay	Max. 8 days
	X		- other criteria: max. 15 days	

### 12.5. ANNUAL SAFETY REPORT

Article R1123-61 of the Public Health Code)

For category 1 research, on the anniversary date of the *research authorisation* the sponsor will write a safety report (or Development Safety Update Report – DSUR) including:

- the list of serious adverse reactions that may be related to the experimental treatment(s) of the research, including expected and unexpected serious reactions, that occurred in the relevant study during the reporting period,
- a concise and critical analysis of the safety of the research participants.
- summary tables of all serious adverse reactions that have occurred in the study since the beginning of the research.

This report is sent to the ANSM and the CPP within 60 days of the anniversary date of the research authorisation.

## 13. STATISTICAL CONSIDERATIONS

## 13.1. SAMPLE SIZE OF THE STUDY

In this trial, patients will be randomly allocated to the two groups with a 1:1 ratio. Randomisation will be stratified based on the presence of a personal history of atopy atopic dermatitis.

For analysis of primary outcome, the percentage change in mTLSS score from baseline to Week 16 will be compared between both groups.

Sample size calculations are based on a clinically meaningful absolute difference between groups in the mean percentage change in mTLSS score from baseline to Week 16 of -25% (greater percentage decrease expected in dupilumab compared with placebo). Assuming a standard deviation of 40% in both groups, sample size of 84 patients (42 by group) will achieve over 80% power to detect such a difference with a significance level (type-I error) of 0.05 using a two-sided two-sample t-test (13).

To account for potential non-evaluable patients estimated to 10%, a total of 94 patients will have to be randomised.

Sample size computations were done using PASS 11. NCSS, LLC. Kaysville, Utah, USA. www.ncss.com.

### 13.2. STATISTICAL ANALYSIS PLAN

A statistical analysis plan (SAP) will be issued and validated by the scientific committee of the study prior to the unblinding of the database. All statistical analyses detailed in the SAP will be conducted by a sponsor statistician using Stata® Version 11.2 or later or SAS® Version 9.3 or later. A single statistical analysis will be conducted at the end of the study.

### 13.3. SUBJECT POPULATIONS FOR ANALYSIS

- The Intention-to-Treat (ITT) population will consist of all randomized patients, independently of whether they receive study treatment or not. Patients will be analysed according to the treatment they were randomised to receive and not according to what they actually received, if different.
- The Per Protocol (PP) population will consist of all randomised patients who are evaluable for primary endpoint and who are considered not to have major protocol deviations (e.g. violation of major eligibility criteria, non-compliance to randomised treatment, use of forbidden drug...). The major protocol violations are patients who do not fulfill the diagnosis criteria for hand dermatitis, patients who have only mild disease at baselines or patients who use systemic immunosuppressants including oral corticosteroids during the study. The major protocol violations will be further defined in the SAP and validated by the coordinating investigator of the study.
- The Treated population will include all randomised patients who receive at least one dose of the study treatment (dupilumab or placebo). Subjects will be analysed according to the actual treatment received.

#### 13.4. STATISTICAL METHODS

## General approach

Study variables will be described by using the appropriate descriptive statistics according to the type of variable:

- Continuous variables: number of non-missing observations, mean, standard deviation, median, first and third quartile, minimum and maximum
- Categorical variables: number of non-missing observations, number and percentages of each modality (percentages will be calculated based on non-missing observations).

Descriptive tables will be displayed for the dupilumab group, for the placebo group and overall. More details on the variables to describe will be provided in the SAP.

## Primary efficacy endpoint analysis

In primary efficacy analysis, the percentage change in mTLSS score from baseline to Week 16 will be compared between both groups using a covariance analysis including the group, the stratification factor (personal history of atopy) and the baseline mTLSS score as covariables. Treatment effect will be tested at a 5% significance level (confirmatory test). The ITT population will be used for this primary efficacy analysis. Missing data on mTLSS score at Week 16 will be replace using the Last-Observation-Carry-Forward (LOCF) imputation method.

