SIZE OF THE STUDY	Sample size calculations are based on a clinically meaningful absolute difference between groups in the mean percentage change in mTLSS score from baseline to Week 16 of -25% (greater percentage decrease expected in dupilumab compared with placebo). Assuming a standard deviation of 40% in both groups, sample size of 84 patients (42 by group) will achieve over 80% power to detect such a difference with a significance level (Type-I error) of 0.05 using a two-sided two-sample t-test.  To account for potential non-evaluable patients estimated to 10%, a total of 94 patients will have to be randomised.
NUMBER OF CENTRES PLANNED	It is a multicenter national study performed in four expert centres in dermato-allergology, where physicians are used to manage patients with moderate to severe CHE.
DURATION OF THE STUDY	Duration of the inclusion period: 54 months.  Duration of each patient's participation: 21 to 24 weeks.  Total duration of the study: 60 months.

STATISTICAL ANALYSIS OF THE DATA	In primary efficacy analysis, the percentage change in mTLSS score from baseline to Week 16 will be compared between both groups using a covariance analysis including the group, the stratification factor (personal history of atopic dermatitis) and the baseline mTLSS score as covariables. Treatment effect will be tested at a 5% significance level (confirmatory test). The ITT population will be used for this primary efficacy analysis. Missing data on mTLSS score at Week 16 will be replaced using the Last-Observation-Carry-Forward (LOCF) imputation method.
EXPECTED CONSEQUENCES	The expected consequences of this study is that a 16-week course of dupilumab will be more effective than placebo for the treatment of moderate to severe CHE not adequately controlled with topical therapy.

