#### 11.7. RULES FOR INTERRUPTING THE STUDY

The end of the study does correspond to the end of study participation.

In line with the current regulation, each patient can at any time withdraw from the study. The participation to this study is voluntary. The patient does not have to provide with any justification for withdrawing his/her participation. If a patient stops the treatment during the study, if he wants, he'll be followed in the study.

The investigator will have to complete an early termination visit sheet in the CRF indicating the reason for interruption of the study: premature discontinuation (efficacy/safety issue), lost to follow-up, withdrawal of consent, major deviation from the protocol.

The subject withdrawing prematurely from the study will not be replaced.

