## Sensitivity analyses on primary efficacy endpoint

Three sensitivity analyses will be performed. In the first, multiple imputations method will be used to handle missing outcomes. In the second, no imputation of missing data will be done meaning that only patients evaluable for primary endpoint among the ITT population will be considered in the analysis. Finally, the efficacy analysis will be done on the Per-Protocol population.

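### LOCF decides the confirmatory Week 16 mTLSS test, so the estimate depends on how many patients leave each arm and when; the multiple imputation already planned should be primary

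*Protocol*

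**What the plan says.** Section 13.4, under the primary efficacy endpoint, specifies an ANCOVA of percentage change in mTLSS at Week 16 in the ITT population, with group, the stratification factor and baseline mTLSS in the model. On the error rate it says: "Treatment effect will be tested at a 5% significance level (confirmatory test". On missing values it says: "Missing data on mTLSS score at Week 16 will be replace using the Last-Observation-Carry-Forward (LOCF) imputation method". The synopsis (section 2) repeats the rule: "Missing data on mTLSS score at Week 16 will be replaced using the Last-Observation-Carry-Forward (LOCF) imputation method". Neither place gives a reason for LOCF or an assumption about who drops out.

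The sensitivity analyses in 13.4 begin with a different method: "In the first, multiple imputations method will be used to handle missing outcomes". An analysis without imputation and a Per-Protocol analysis follow.

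The follow-up table (11.2) schedules mTLSS at Day 0 and Weeks 4, 8, 12 and 16. On patients who stop injections, section 11.7 says: "If a patient stops the treatment during the study, if he wants, he'll be followed in the study". Section 13.1 allows for 10% non-evaluable patients overall and gives no split by arm.

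**The concern.** The protocol expects improvement over the treatment period, and the two arms are expected to differ in how much they improve. LOCF freezes a patient who leaves at the last value seen and treats that value as a measured Week 16 result. If patients would have gone on improving, the carried value is too poor. The shortfall is larger the earlier the patient leaves, and larger in the arm that improves more. The arm difference therefore shifts with the dropout pattern, and the imputed values are analysed with no allowance for their uncertainty.

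Unequal dropout is plausible on the protocol's own terms. Section 11.7 lists efficacy and safety problems as reasons for stopping, and such reasons need not be balanced between placebo and an active drug. At stake are the size of the reported effect, the power, and to a lesser degree the type I error of the one test that decides the trial. The planned multiple imputation would show a discrepancy, but as a sensitivity analysis it would not change the confirmatory result.

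**Working it through.** **The plan's own figure.** Section 13.1 states that a "sample size of 84 patients (42 by group) will achieve over 80% power to detect such a difference". Inputs: difference 25, SD 40, two-sided 5%.
- Normal approximation: n = 2 × (1.960 + 0.842)² × 40² / 25² = 40.2, so 41 per group.
- Exact t-test power is 79.8% at 41 and 80.8% at 42, so 42 per group is right.
- 84 / 0.90 = 93.3, so 94 randomised. The sample size reproduces and is not in question.

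**Assumptions for the LOCF check (not from the protocol).**
- Mean placebo change at Weeks 4, 8, 12 and 16: A) -10, -17, -22, -25, or B) -15, -26, -34, -40.
- A true effect of -25 builds as -10, -17, -22, -25.
- A dropout's last value is at baseline, Week 4, 8 or 12 in 10%, 40%, 30% and 20% of cases. For a patient with no later visit, baseline (0% change) is carried.
- Dropout is unrelated to outcome.

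**Expected bias by hand.** Let g be the mean improvement still to come when a patient leaves.
- Placebo A: 0.1×25 + 0.4×15 + 0.3×8 + 0.2×3 = 11.5
- Placebo B: 0.1×40 + 0.4×25 + 0.3×14 + 0.2×6 = 19.4
- The true effect adds 11.5 (same steps as A), so dupilumab has g = 23.0 (A) or 30.9 (B).

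Expected LOCF difference = true difference + d_D × g_D − d_P × g_P, where d_D and d_P are the dropout proportions on dupilumab and placebo.

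| True effect | Dropout, placebo / dupilumab | A | B |
|---|---|---|---|
| -25 | 10% / 10% | -25 + 2.30 − 1.15 = -23.85 | -25 + 3.09 − 1.94 = -23.85 |
| -25 | 5% / 15% | -25 + 3.45 − 0.575 = -22.1 | -25 + 4.635 − 0.97 = -21.3 |
| 0 | 10% / 10% | 0 | 0 |
| 0 | 15% / 5% | 0.575 − 1.725 = -1.15 | 0.97 − 2.91 = -1.94 |
| 0 | 30% / 5% | 0.575 − 3.45 = -2.9 | 0.97 − 5.82 = -4.85 |

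**Power and type I error by simulation.** 47 per arm, SD 40 at each visit, correlation 0.7, two-sided 5% t-test, 20,000 trials per scenario. Ranges cover A and B.

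| True effect | Dropout, placebo / dupilumab | LOCF rejects | Observed cases reject |
|---|---|---|---|
| -25 | 10% / 10% | 80-81% | 81% |
| -25 | 5% / 15% | 71-75% | 81% |
| 0 | 10% / 10% | 4.8-5.2% | 4.7-5.1% |
| 0 | 15% / 5% | 5.0-5.6% | 4.9-5.0% |
| 0 | 30% / 5% | 6.1-8.7% | 5.0% |

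The simulated mean differences agree with the hand calculation to within about 0.1 point.

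**Dependence on the assumptions.** A second model used SDs of 25, 32, 37 and 40 over the visits, serial correlation 0.8, Week 16 changes of -30% to -50%, and dropout either spread evenly over time or concentrated early. A 15% / 5% split with no effect gave a spurious -1.5 to -4.0 points and rejection of 5.1-7.8%. A 5% / 15% split with a true -25 gave -19.6 to -21.5 and power of 64-74%. With ANCOVA in place of the t-test (correlation 0.7), the 5% / 15% split gave -21.5 to -22.4 and power of 72-77%. Regression imputation from the Week 4 to 12 values returned about -25.0 to -25.2.

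**The case against.** The strongest reply is that little happens at the attrition the protocol plans for. With 10% in each arm and no true effect, LOCF is unbiased and the error rate stays at about 5%. With a true -25 it costs about one point and almost no power relative to observed cases. Multiple imputation and an analysis without imputation are both prespecified, so an artefact would be visible. This stands, and it limits the severity. It does not remove the point, because LOCF still decides the test if the analyses disagree.

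A reader might infer more than the documents support:
- **That type I error is clearly inflated.** In the main model about 9% needs a split such as 30% against 5%, which nothing in the protocol suggests.
- **That LOCF takes power from 85% down to 71-75%.** The 85% is the power of all 94 patients with no missing data, which no method restores. The fair comparator at the same dropout is about 81%.
- **That more placebo dropout always favours dupilumab.** This holds if dropout is unrelated to outcome and patients would have kept improving. If placebo patients leave during a flare, their unseen Week 16 value may be as bad as the value carried, or worse.
- **That a missing-not-at-random or tipping-point analysis has been omitted.** Section 13.2 promises an SAP, which is not at hand and may contain one.
- **That baseline is carried when no later visit exists.** Section 13.4 does not say so; this is an assumption of the check.

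The remark in 13.4 that this is not a confirmatory phase III study concerns multiplicity of the secondary endpoints. The same section calls the primary test confirmatory.

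**Conclusion.** The concern holds at should-fix level. LOCF as the primary rule makes the Week 16 estimate depend on the dropout pattern, and its direction cannot be relied on as conservative. At 10% attrition overall, the consequence ranges from about one point of attenuation with equal dropout to about three or four points, and some 6 to 10 percentage points of power, when dupilumab loses three times as many patients as placebo. With no true effect and the opposite split, the spurious benefit is 1 to 2 points and the error rate about 5-6%. A harsher set of assumptions raises these to 4 points and 7.8%. All of these rest on assumed arm splits, trajectories and correlations and on dropout unrelated to outcome; the protocol fixes only the 10%. The sample size of 84 evaluable and 94 randomised patients is correct.

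**What to change.** Before unblinding, exchange the roles of the two methods already in section 13.4. Make the primary analysis either of the following:
- the same ANCOVA after multiple imputation, with Week 16 mTLSS imputed from group, the stratification factor, baseline and the Week 4, 8 and 12 scores; or
- an MMRM on percentage change at Weeks 4, 8, 12 and 16, with the Week 16 contrast as the test.

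Move LOCF to the sensitivity analyses and make the same change in the synopsis. Both options assume missing at random, which should be stated.

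The cost is a short amendment, matching SAP wording and slightly more modelling. All the scores are already scheduled, and the sample size does not change.

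Seeking the Week 16 score by default from patients who stop injections without withdrawing consent would also help, but that is a change in data collection. Inclusion began in July 2019 for 54 months, so to about January 2024, and version 6.0 is dated June 2023. Such a change would reach few patients, and the correction does not depend on it.

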## Sensitivity analyses on primary efficacy endpoint

Three sensitivity analyses will be performed. In the first, multiple imputations method will be used to handle missing outcomes. In the second, no imputation of missing data will be done meaning that only patients evaluable for primary endpoint among the ITT population will be considered in the analysis. Finally, the efficacy analysis will be done on the Per-Protocol population.

## Secondary efficacy endpoints analysis

Secondary efficacy endpoints will be tested without adjusting for multiplicity. There will be no fixed order of endpoints as this study is not considered a confirmatory phase III study.

The treatment effect on continuous secondary endpoints (i.e. change from baseline to Week 16 of pruritus, pain, quality of life, WPAI and EASI scores) will be estimated and tested using a covariance analysis including the group, the stratification factor and the baseline scores as covariables.

The treatment effect on binary secondary endpoints (i.e. clearance or almost clearance of CHE at Week-16 based on IGA or PaGa) will be estimated and tested using a Cochran Mantel-Haenszel test adjusted on the stratification factor used for randomization.

Secondary efficacy analyses will be performed on the Intention-To-Treat population. Methods to deal with missing data will be described in the SAP.

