- Randomisation will be stratified based on the presence of a personal history of atopic dermatitis as it is expected to be the major factor potentially influencing the primary end point. Baseline severity is not expected to influence the primary end-point as relative change in mTLSS is not expected to be influenced by disease severity.

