#### 5.2. RANDOMISATION METHODS

Patients will be randomly assigned in a 1:1 ratio into the dupilumab or the placebo group using a computer-generated randomization sequence with permuted-blocks. The randomization will be stratified on the most important parameter potentially influencing outcome: the presence or not of a personal history of atopic dermatitis.

The randomization list will be established by an independent statistician at Toulouse hospital not involved in the trial before the start of the study.

Patients will be randomized on Day 0 visit by the investigators using the "randomization" web page of the eCRF after signatory of informed consent and eligibility criteria check. After validating the content, the site immediately communicates to the investigator and to the pharmacy the patient's unique randomization number in the study as result of the randomization.

A document describing the randomization procedure will be kept confidentially in the Biostatistic Unit (USMR du CHU de Toulouse).

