# 6. ELIGIBILITY CRITERIA

#### 6.1. INCLUSION CRITERIA

- Adult Patients (≥18 years) affiliated to a social insurance protection regimen.
- Patients with moderate to severe chronic ( $\geq 6$  months) hand eczema with an Investigator global assessment (IGA) of 3 or 4 (out of a scale of 0 to 4).
- Patients intolerant (according to the physician) or resistant to highly potent topical corticosteroids. Inadequate response (resistance) to highly potent topical corticosteroids is defined as a history of failure to achieve and maintain remission or a low disease activity state (comparable to an IGA score of 0 [indicating clear] to 2 [indicating mild]) despite treatment with a daily regimen of highly potent topical corticosteroids applied for 14 days or for the maximum duration recommended for highly potent topical corticosteroids.
- Patients who are able to understand the study procedures including the ability to complete patientoriented questionnaires.
- Patients who are able to apply a stable dose of emollients within 7 days before the baseline visit.
- Patients who agree to sign the written informed consent.

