#### 10.2. SECONDARY JUDGEMENT CRITERIA

- Evolution of pruritus associated with CHE at week 16 since baseline measured with a visual analog scale.
- Evolution of pain associated with CHE at week 16 since baseline measured with a visual analog scale.
- Improvement of quality of life at week 16 since baseline measured by DLQI (Dermatology Life Quality Index) and EQ-5D.
- Evolution of sleep loss associated with CHE at week 16 since baseline measured with a visual analog scale.
- Clearance or almost clearance of hand eczema at week 16 as defined by an Investigator's global assessment (IGA) of 0 or 1.
- Clearance or almost clearance of hand eczema at week 16 as assessed by the Patient's global assessment (PaGa) of 0 or 1.
- Improvement of work productivity at week 16 since baseline as assessed by the WPAI questionnaire (Work Productivity and Activity Impairment).
- Evolution of the Eczema Area and Severity Index at week 16 since baseline in patients who have eczema on other parts of the body than the hands.
- The safety throughout the course of the study (at 20 weeks since baseline) by monitoring adverse events, serious adverse events, injection site reactions.
- The evolution of laboratory parameters (full blood count, total IgE and specific IgE) at week 16 since baseline.

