# DUPECZEMAIN RC31/18/0269 - Version $n^{\circ}$ 6.0

Phase	Screening		Treatment period								Follow up period
Visit	Screening	V1	(V2)	V3	(V4)	V5	(V6)	V7	(V8)	V9	V10 FU Visit
Day/Week	Up to 4 weeks prior to Visit 1	Day 0	Week 2	Week 4	Week 6	Week 8	Week 10	Week 12	Week 14	Week 16	Week 20
Visit window (days)			±3	±3	±3	±3	±3	±3	±3	±3	±3
Laboratory – Biochemistry (fasting)		X								X	
Laboratory full blood count	X									X	
Laboratory screening for hepatitis B, C and HIV	X										
Laboratory including specific IgE dosage (only Toulouse site)		X								X	
Laboratory including Total IgE dosage		X								X	
Pregnancy test*	X	X		X		X		X		X	X
Vital signs (BP, pulse, temperature)		X									
Photographs		X				X				X	

Phase	Screening	Treatment period									
Visit	Screening	V1	(V2)	V3	(V4)	V5	(V6)	V7	(V8)	V9	v10 FU Visit
Day/Week	Up to 4 weeks prior to Visit 1	Day 0	Week 2	Week 4	Week 6	Week 8	Week 10	Week 12	Week 14	Week 16	Week 20
Visit window (days)			±3	±3	±3	±3	±3	±3	±3	±3	±3
Patients Global Assessment of disease severity		X		X		X		X		X	
Investigator's Global Assessment of disease severity		X		X		X		X		X	
EASI		X		X		X		X		X	
mTLSS		X		X		X		X		X	
Hand eczema pruritus by VAS		X		X		X		X		X	
Hand eczema Sleep loss by VAS		X		X		X		X		X	
Hand eczema Pain assessment by VAS		X		X		X		X		X	
DLQI		X		X		X		X		X	
EQ-5D-5L		X		X		X		X		X	
WPAI		X								X	
Skin Biopsy (sub study only)		X								X	
Removal of the stitches (sub study only)			X								
Blood sample for sub study		X								X	
Subject treatment instructions		X									
Study treatment administration		X	(X)	X	(X)	X	(X)	X	(X)		

\*Serum pregnancy test required at Screening visit and V9, urinary pregnancy test will be performed at V1, V3, 5, 7 and 10

Each visit will be conducted by the investigator (Dermatologist, Allergologist) at the dermatology outpatient clinic in the participating centers.

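### The IGA 0/1 and PaGa 0/1 tests adjust for atopic dermatitis history only and leave collected baseline severity unused: a valid test, but some precision may be lost

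*Protocol*

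**What the plan says.** - **Endpoints.** Section 10.2 defines clearance at week 16 "as defined by an Investigator's global assessment (IGA) of 0 or 1" and, for the patient, "as assessed by the Patient's global assessment (PaGa) of 0 or 1". Both are absolute thresholds. Section 4.2 makes clearance, by investigator and by patient, an objective to be demonstrated.
- **Binary analysis.** Under the secondary efficacy endpoints heading of section 13.4, the effect on these endpoints "will be estimated and tested using a Cochran Mantel-Haenszel test adjusted on the stratification factor used for randomization". Section 5.2 gives that factor as "the presence or not of a personal history of atopic dermatitis". It is the only one.
- **Other efficacy analyses.** The same part of 13.4 analyses the continuous secondary endpoints by "covariance analysis including the group, the stratification factor and the baseline scores as covariables". The primary analysis includes baseline mTLSS.
- **Baseline data.** Section 6.1 admits patients who have "hand eczema with an Investigator global assessment (IGA) of 3 or 4 (out of a scale of 0 to 4", so baseline IGA takes two values. The follow-up table in section 11.2 marks the row "Investigator's Global Assessment of disease severity" and the corresponding patient row at V1.
- **Status.** Section 13.4 applies no multiplicity control to the secondary endpoints and does not regard the study as confirmatory phase III.

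**The concern.** Of the efficacy analyses set out in section 13.4, the two clearance tests are the only ones without a baseline term. Yet a baseline score could plausibly matter for them: to reach IGA 1, a patient who starts at 4 must fall three grades and one who starts at 3 must fall two. Randomisation does not balance baseline IGA, because it is not a stratification factor.

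If baseline severity predicts clearance, two things follow. The confidence interval for the clearance difference is wider than it need be. And when one arm happens to receive more IGA 4 patients, the reported difference moves with that imbalance. The baseline values needed to deal with both are already collected.

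**Working it through.** **The plan's own figure.** The only stated power concerns the primary endpoint. A difference of 25 points with SD 40 and 42 per group gives 80.8% by the exact two-sided t-test, and 84/0.9 = 93.3 rounds up to 94. Both figures in section 13.1 reproduce. The protocol gives no power or precision figure for the binary endpoints.

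**Inputs for the binary endpoints.** From the protocol: 94 randomised 1:1 (47 per arm, all analysed) and about 40% clearance on dupilumab (section 3.4). Assumed, because the protocol does not give them: placebo clearance 15% (range 10-20%), 40% of patients at IGA 4 (range 30-50%), AD history in 60% with no effect on clearance, and an odds ratio of clearance for IGA 4 versus 3 from 1.0 to 0.2.

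**Standard error.** sqrt(0.40×0.60/47 + 0.15×0.85/47) = sqrt(0.00782) = 0.088, about 9 points.

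**Chance imbalance in IGA 4 share.** SD of the between-arm difference = sqrt(2×0.40×0.60/47) = 0.101. A difference of 10 points or more occurs in about 34% of trials.

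**Carry-over of imbalance.** The shift per 10 points is roughly 0.10 × the average over the two arms of (clearance at IGA 3 − clearance at IGA 4). Example with 40% vs 20% clearance:
- odds ratio 0.5: rates 46/30% and 24/14%; 0.10 × (16+10)/2 = 1.3 points
- odds ratio 0.33: rates 50/25% and 26/11%; 0.10 × (25+15)/2 = 2.0 points
- odds ratio 0.2: rates 54/19% and 28/7%; 0.10 × (35+21)/2 = 2.8 points

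Simulation gives 1.3, 2.0 and 2.9 for these, and about 0 once IGA is a stratum.

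**Power and variance, IGA 0/1.** Simulation, 40,000 trials per scenario, 40% vs 15% clearance, 40% at IGA 4. The variance ratio is AD only divided by AD × IGA, for the Mantel-Haenszel risk difference.

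| Odds ratio, IGA 4 vs 3 | Power, AD only | Power, AD × IGA | Change | Variance ratio | Shift per 10 points of imbalance |
|---|---|---|---|---|---|
| 1.0 | 79.2% | 78.4% | -0.8 | 0.98 | about 0 |
| 0.5 | 79.2% | 79.0% | -0.2 | 0.995 | 1.2 |
| 0.33 | 78.9% | 80.0% | +1.1 | 1.02 | 1.8 |
| 0.2 | 79.1% | 81.7% | +2.6 | 1.07 | 2.6 |

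The largest gain in this range is at odds ratio 0.2 with 50% at IGA 4: 78.8% to 82.2%, variance ratio 1.09. Type I error is 4.9-5.1% for both tests.

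**An extreme gradient.** Take clearance of 62/12% on dupilumab and 28/3% on placebo for IGA 3/4. The odds ratios are (0.12/0.88)/(0.62/0.38) = 0.084 and (0.03/0.97)/(0.28/0.72) = 0.080. With 70% AD history, power goes from 73.0% to 80.1% at 40% IGA 4, and from 66.1% to 74.5% at 50%. Gains of this size need roughly a 12-fold odds gradient.

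**Stratum size.** With 70% AD history (the figure in the section 2 summary) and 40% at IGA 4, the smallest of four strata has 94 × 0.30 × 0.40 = 11.3 patients, 5 or 6 per arm.

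**PaGa.** No simulation covers PaGa. Sections 6.1 and 6.2 do not restrict baseline PaGa, so the IGA figures do not transfer to it.

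**The case against.** The strongest reply is that nothing here is an error. Stratifying the test on the randomisation factor matches analysis to design. Type I error holds, the estimate is unbiased over randomisations, and chance imbalance is ordinary sampling variation already covered by the confidence interval. The endpoints are non-confirmatory, the trial is sized on the primary endpoint only, and a supportive adjusted analysis could sit in the statistical analysis plan. All of this stands, and it limits the point to efficiency and consistency. It does not explain why a collected baseline value is used in the other efficacy analyses and not here, and the protocol itself fixes the test.

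A reader might make three stronger inferences that the documents do not support:
- **That precision is certainly lost.** This depends on how strongly IGA 3 versus 4 predicts clearance, which the protocol does not state. With a weak or absent gradient the added strata cost a little power. Section 5.2 names AD history, not severity, as the most important factor for outcome.
- **That section 3.3 wrongly justifies the test.** It says "Baseline severity is not expected to influence the primary end-point as relative change in mTLSS is not expected to be influenced by disease severity", but in explaining why randomisation is stratified on AD history and not on severity. The protocol never offers it as a reason for leaving severity out of this analysis. It is fair only to note that an argument about relative change says nothing about an absolute threshold.
- **That the same gain applies to PaGa.** That was not examined.

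**Conclusion.** The point holds as a modest improvement, not as a correction of an invalid analysis. The asymmetry within section 13.4 and the unused baseline values are plain from the text. The benefit is uncertain: for IGA 0/1 the expected change in power is about -1 to +3 points for severity odds ratios from 1.0 to 0.2, and clearly more only near 0.08. Protection against imbalance is real but small relative to the standard error. These sizes rest on assumed placebo clearance, IGA 4 share and severity gradient; only the 40% dupilumab rate and the 94 patients come from the protocol. For PaGa 0/1 the argument is qualitative.

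**What to change.** In section 13.4, or in the statistical analysis plan before unblinding:
- **IGA 0/1.** Stratify the Cochran-Mantel-Haenszel test by AD history × baseline IGA (3 vs 4), and report the Mantel-Haenszel risk difference with 95% CI from the same strata. The risk difference is collapsible, so the quantity estimated does not change.
- **PaGa 0/1.** Adjust for baseline PaGa as a covariate, for example by logistic regression with group, AD history and baseline PaGa, reported as a standardised risk difference. Splitting baseline PaGa at 0-3 versus 4 would be arbitrary and would pool any patient already at 0 or 1 with those at 3.

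The cost is a sentence or two and no new data. The downside is smaller strata (about 11 patients in the smallest) and up to about 1 point of power if baseline severity turns out not to be prognostic. The choice should be fixed before unblinding, because adding baseline severity afterwards would look post hoc.
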